3.3 Study Measures

AIM 1 Pilot study:

- **E-triage:** The e-triage will consist of 16 questions, modified from the validated NCI Pro-CTCAE™, which will be sent to patients via WaytoHealth®'s two-way texting system 96 hours prior to their scheduled immunotherapy infusion (see appendix B). Questions will pertain to common or emergent immune related adverse events as defined by the NCCN guidelines and two senior disease experts⁴²⁻⁴⁴. Patients will be prompted via text to measure the presence and severity of symptoms over the week prior. A final question will be included to capture any additional symptoms patients wish to disclose.
- **NCI Pro-CTCAE™:** A subset of patients may be asked to fill out a subset of the NCI PRO-CTCAE™, a set of validated questions for the collection of patient-reported outcomes to capture symptomatic adverse events in patients on cancer clinical trials, in order assess construct validity.
- **Definition of gold standard:** Patient reported toxicity captured by the text-based instrument will be compared to provider reported toxicity as documented in the EMR as the gold standard. To assess provider reported toxicity, standardized abstraction protocols will be developed by the PI and implemented by trained research staff.

AIM 2 Randomized control study:

- **Care time:** Care time will be defined as total time spent commuting to and receiving cancer care (including time spent obtaining labs). This will be captured using a combination of time-stamp information abstracted from AirFinder®, a real time patient located system deployed in the Perelman Cancer Clinics, and self-reported time for commuting and time spent obtaining local labs. Commute times will also be estimated using the patient's home address geocoded using ArcGIS software.
- **Emergency department and hospitalization rates:** Total number of emergency department visits and hospitalizations will be collected using data abstracted from the Penn electronic medical record during a 3 month follow-up window as well as through patient check-ins with study staff during routine infusion visits to account for care received outside the Penn system.

CONFIDENTIAL

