3.4.1 Primary Study Endpoint

AIM 1 Pilot: To assess the performance of the text-based e-triage system sensitivity and specificity with a gold standard will be determined.

AIM 2 Randomized control trial: The primary endpoint will be cumulative care time associated with cancer treatment, measured over a over three months or at least 3 infusion visits. We will define care time as total time spent commuting to and receiving care (including time spent obtaining labs).

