3.4.2 Secondary Study Endpoints

AIM 2 Randomized control trial: Secondary endpoints will include total wait time (see attached study flowchart), total number of ED visits and/or hospitalizations, health related quality of life utilizing the FACT-G⁴, treatment satisfaction with the PSQ-18¹, and providers satisfaction using the net-promoter score^{2,3}.

4 Study Population and Duration of Participation

4.1 *Duration of Study Participation*

AIM 1 Pilot study: The duration of study participation will be 2 months from the date of enrollment.

AIM 2 Randomized control study: The duration of study participation will be the time it takes to complete 3 infusion visits, approximately 3 months..

4.2 *Total Number of Subjects and Sites*

Penn (Perelman Center for Advanced Medicine floors 2,3,4) will be the only site recruiting patients. For the pilot study we will enroll up to 100 patients over a 2-months. For the randomized control trial, to have 160 evaluable subjects, with an expected 10% drop out rate, we plan to enroll 176 patients.

4.3 *Inclusion Criteria*

AIM 1: Pilot participants:

- Over 18 years of age
- Access to mobile device with text messaging capabilities
- Receiving single agent PDL-1/PD-1 targeted immune checkpoint blockade for any solid malignancy
- Treating oncologist is at Penn's Abramson Cancer Center

AIM 2: Randomized control trial participants:

- Over 18 years of age

CONFIDENTIAL

- Receiving single agent PDL-1/PD-1 targeted immune checkpoint blockade for any solid malignancy
- Access to and ability to use a mobile phone with texting capabilities

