7.4.2 Data and Safety Monitoring Plan

Overall data and safety will be monitored on an ongoing basis by the PIs and the study team. As needed, the investigators may decide to appoint an independent medical monitor to evaluate adverse events and make recommendations for continuing or stopping a trial. No interim analysis will be conducted.

Monitoring e-triage: All Waytohealth© interactions will be input into a flowsheet embedded into the patient's EMR and available to all study and clinical staff. All relevant persons will be notified via an EMR alert when any new information is entered. Dedicated research staff will be monitoring for inputs daily and will interphase with the research PI as well as clinical team as needed for unanticipated responses or symptoms. Any identified symptom will require the patient to have an in-person assessment with their routine clinical team. Clinical staff will be notified of the patient's triage status and offered the opportunity to mandate an in-person assessment regardless of the patient's triage status. A patient's enrollment in the study will be terminated if they experience an emergency medical situation requiring intervention or violate study protocol.

Monitoring clinical events: Research staff will see patients at each of their infusion visits. During this time, they will assess for any unidentified immunotherapy adverse events as well as screen for any emergency department visits or hospitalizations which occurred outside the Penn system. Additionally, research staff will receive EPIC alerts corresponding to any emergency department visits or hospitalizations.

8 Study Administration, Data Handling and Record Keeping

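### Ending enrollment after an emergency or protocol violation leaves care time and outside-Penn events uncollected, which does not fit a three-month intent-to-treat comparison

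*Protocol*

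**What the plan says.** **The rule.** Protocol 7.4.2, under the paragraph on monitoring the e-triage, says a patient's "enrollment in the study will be terminated if they experience an emergency medical situation requiring intervention or violate study protocol". The wording is mandatory and names no arm.

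**The endpoints.** The primary endpoint (Protocol 3.4.1) is "cumulative care time associated with cancer treatment", and Protocol 5.3 counts every unscheduled visit towards it. ED visits and hospitalizations are a secondary endpoint (3.4.2). The primary analysis is intent-to-treat on total care time over three months (Protocol 6.3.2, SAP 1.3.2).

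**The data sources (Protocol 3.3).**
- Time in clinic comes from location time stamps.
- Commute and outside laboratory time come from "self-reported time for commuting and time spent obtaining local labs". In addition, "Commute times will also be estimated using the patient's home address geocoded using ArcGIS software".
- Counts of ED visits and hospital stays "will be collected using data abstracted from the Penn electronic medical record during a 3 month follow-up window". Events at other institutions are learned only when staff speak with the patient at an infusion visit.
- Protocol 7.4.2 adds that "research staff will receive EPIC alerts corresponding to any emergency department visits or hospitalizations".

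**After an early exit.** Protocol 5.4 and 5.4.1 describe one final visit for questionnaires, adverse events and the reason for leaving. Protocol 7.2 follows ongoing serious adverse events. Protocol 8.1 seeks at least vital status when authorization is revoked.

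**The sample size.** Protocol 4.2 enrolls 176 patients "to have 160 evaluable subjects, with an expected 10% drop out rate".

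**The concern.** An emergency that needs intervention is not an incidental reason for leaving. It adds care time and may itself be an ED visit or hospitalization. A rule that ends enrollment at that point stops observation because of what happened after randomization, on the outcomes being compared. Randomization does not protect against that.

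The plan also does not say whether a terminated patient enters the analysis with a shortened total or counts as a dropout from the evaluable number. A shortened total looks like time saved. If terminations were more frequent in one arm, that arm would appear to need less care time for a reason unrelated to avoided office visits.

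Two points of wording add to the uncertainty:
- The rule stands under e-triage monitoring, yet names no arm, and Protocol 8.1 enrolls all subjects on the texting platform. Both arms is the more natural reading, but it is not stated.
- For protocol violators, 7.4.2 makes termination mandatory, while 5.4 leaves withdrawal to the investigator's discretion.

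**Working it through.** **1. What is still collected after termination, as written**

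| Component | Planned source | Continued after termination? |
|---|---|---|
| Clinic time | Location time stamps (3.3) | Not stated |
| Local-lab time | Self-report (3.3) | Not stated |
| Commute | Self-report or geocoding (3.3) | Geocoding possible, for known visits only |
| Penn ED and hospital events | EMR over 3 months (3.3), alerts (7.4.2) | Probably yes |
| Outside-Penn events | Check-ins at infusion visits (3.3, 7.4.2) | Not stated |

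**2. The plan's own power figure.** Inputs from Protocol 6.1 and SAP 1.1: control mean 130 h, SD 118, 40% reduction (52 h), 80 per arm, alpha 0.05 (two-sided assumed).
- Standard error = 118 × √(2/80) = 18.66 h, and 52/18.66 = 2.787.
- Normal approximation: Φ(2.787 − 1.96) = 79.6%. Two-sample t test: 79.1%.
- The stated 79% reproduces.

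**3. How much care time is cut off.** The documents give no emergency rate. I take the planned 10% total dropout as an anchor and assume that half of it (5%) or all of it (10%) is emergency termination. Let p be the share terminated and L = −ln(1 − p). With a constant rate, care time accruing evenly, and the hours of the triggering emergency counted, the retained fraction of mean care time is f = (1 − exp(−L))/L.

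| p | L | f | 130 h becomes | 52 h becomes |
|---|---|---|---|---|
| 5% | 0.0513 | 0.975 | 126.7 h | 50.7 h |
| 10% | 0.1054 | 0.949 | 123.4 h | 49.4 h |

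If routine time falls at three visits instead of evenly, the fraction retained at 10% is the mean of exp(−L·t) over the visit times:
- 0.966 for visits at 0, 1/3 and 2/3 of the window
- 0.950 for visits at 0, 1/2 and 1
- 0.933 for visits at 1/3, 2/3 and 1

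Routine time is therefore cut by about 3% to 7%.

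**4. Rule in both arms, equal rates.** With no true effect both means shrink alike, so no false benefit arises. With the planned effect and SD held at 118, t-test power is 77.1% (5%) or 74.9% (10%). A simulation of 40,000 trials lets the spread change with the truncation. It uses 80 per arm, gamma routine time, an assumed exponential hospital stay with mean 36 h, and total SD 118. It gives 77.6% and 77.2%, against 78.2% and 78.9% without truncation. With no true effect, the simulated total rejection rate is 5.0% and 4.7%.

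**5. Rule in the e-triage arm only, no true benefit.**
- 5%: shift 130 − 126.7 = 3.3 h, and 3.3/18.66 = 0.177. P(Z > 1.96 − 0.177) = 3.7%.
- 10%: shift 130 − 123.4 = 6.6 h, and 6.6/18.66 = 0.354. P(Z > 1.96 − 0.354) = 5.4%.
- Simulation: 3.7% and 5.6%. The nominal figure in this direction is 2.5%.

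**6. Rule in both arms, unequal rates, no true benefit.** Assume 5% terminated in control and 15% in e-triage, each losing half the window's care time.
- Control: 130 × (1 − 0.05 × 0.5) = 126.75 h.
- E-triage: 130 × (1 − 0.15 × 0.5) = 120.25 h.
- The apparent saving is 6.5 h, or 13 h if terminated patients use twice the mean care time.

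**7. Terminated patients removed as non-evaluable, on top of the planned dropout.** A further 5% loss (80 × 0.95 = 76 per arm) gives 77.0% power by t test. A further 10% (80 × 0.90 = 72 per arm) gives 74.7%.

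**The case against.** The best case on the other side is that the data loss is inferred from silence. Section 7.4.2 ends enrollment; it does not say that outcome collection stops. The three-month EMR window and the rule counting unscheduled visits carry no exception for terminated patients. The paragraph after the rule has staff screen for ED visits and hospitalizations at infusion visits, so some patients must be expected to stay on study after such an event. The triggering emergency is undefined and may be narrower than the secondary endpoint. Sections 5.4 and 5.4.1 are written for patients who withdraw early or withdraw consent, not expressly for imposed termination. The consent form and the flowchart are not in the documents under review.

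The size is also small. A 10% dropout is already budgeted, and terminations may fall within it, since progression and change of therapy are only examples. Under the more natural both-arms reading with equal rates, the loss is a few points of power at most.

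Much of this stands: the overlap with the endpoint is of unknown frequency, every rate above is assumed, and the worst figures need the less natural reading or unequal rates. It does not remove the point. If sections 5.4 and 5.4.1 do not cover these patients, the plan describes even less follow-up for them. Nothing in the text continues time stamps, local-lab time or outside-Penn check-ins. Intent-to-treat says who is analysed and in which arm; it does not supply totals that were never collected.

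**Conclusion.** The concern holds, and it should be fixed at medium confidence. The termination rule, followed as written, cuts off parts of the primary and secondary endpoints because of an event related to them, and the plan has no provision for the missing follow-up or for analysing shortened totals.

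The likely effect is modest. With 5% to 10% terminated equally in both arms, it is a few points of power and no false benefit. A false benefit needs the rule to act only, or more often, in the e-triage arm. These sizes rest on assumed termination rates, a constant rate over the window, and unchanged accrual of care time after an emergency. The plan's 79% power is not in error. The case for acting is that the trigger is an outcome under study, the lost data cannot be rebuilt at analysis, and the remedy is cheap.

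**What to change.** 1. Reconcile Protocol 7.4.2 with 5.4, 5.4.1, 3.3, 3.4.1, 5.3 and 6.3.2. State which arms the rule covers, and whether termination of protocol violators is mandatory or discretionary. When e-triage use stops clinically is for the sponsor to decide.
2. State that termination does not end outcome data collection. For every randomized patient in both arms, continue to the end of the window:
   - care time: time stamps, commute (geocoded or self-reported) and local-lab time
   - ED visits and hospitalizations: Penn EMR and alerts, plus brief check-ins for care outside Penn.

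   The exception is withdrawal of consent to data collection or of authorization (Protocol 8.1).
3. Define the end of that window in the same terms throughout. Protocol 3.4.1 allows three months or at least three infusion visits, 4.1 uses completion of three infusions, and 6.3.2 and SAP 1.3.2 use three months.
4. In the SAP, analyse all randomized patients as assigned, say how incomplete totals are handled, and report terminations by arm and reason.

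The cost is Protocol and SAP wording, a check that the consent form covers continued collection, some extra abstraction, and short check-ins by existing staff when no infusion visit takes place. Penn events and geocoded commute use sources already planned.

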8.1 Confidentiality

Information about study subjects will be kept confidential and managed according to the requirements of the Health Insurance Portability and Accountability Act of 1996 (HIPAA). Name, date of birth, and medical record number will be the only protected health information collected during this study. All PHI within the secure research database will be encrypted. All study participants will be assigned a unique study ID. All study information will be stored in locked file cabinets and in password-protected computer files. Only authorized study personnel will have access to these files.

The database (RedCap) will be used to track patient information will be encrypted to hide patient identifiers (such as name, address, birth date and phone number), allowing for the conducting of research without endangering subjects personal privacy.

All subjects will be enrolled on WaytoHealth©. The e-triage will be executed using WaytoHealth©'s platform which uses a role-based access control (RBAC) approach to assure that participant confidentiality and study integrity is preserved. Access and visibility is primarily governed by the role of the individual accessing the system. Access is granted by invitation only and can be revoked at any time. All WaytoHealth© servers are managed by Penn Medicine Academic Compute Services (PMACs). All data at-rest is stored on encrypted disks using encryption keys managed by WaytoHealth©. Encrypted disks use AES encryption with a minimum of 256-bit keys, or keys and ciphers of equivalent or higher cryptographic strength. User passwords are never stored in clear text; they are "salted" and "hashed" to eliminate data leakage. All data transmission is encrypted end to end using encryption keys managed by WaytoHealth©. Transmission encryption keys use a minimum of 2048-bit RSA keys, or keys and ciphers of equivalent or higher cryptographic strength (e.g., 256-bit AES session keys in the case of IPsec encryption). Data downloads are generally prohibited by policy. Where appropriate, most datasets are blinded of all personally identifiable information when exported for analysis. A limited number of exports including identifiers exist to assist research staff with recruitment tracking and study management efforts.

CONFIDENTIAL

These datasets are only accessible to certain user roles. These user roles are required to sign and adhere to a W2H Security Agreement as described in appendix C.

In the event that a patient revokes authorization to collect or use PHI (which will be encrypted from the specimen(s) and other health data), the Investigator, by regulation, retains the ability to use all information collected prior to the revocation of patient authorization. For patients that have revoked authorization to collect or use PHI, attempts should be made to obtain permission to collect at least vital status (i.e. that the patient is alive). This data will not become part of the study subjects' permanent record, such as employment or academic record.

8.2 Data Collection and Management

All study participants will be assigned a unique study ID. The Research Electronic Data Capture (REDCap) system will be used to autogenerate the participant identifier and track patient information. Data is encrypted to hide patient identifies (such as name, address, birth date, and phone number), allowing for the conducting of research without endangering subject's personal privacy. All clinical data is entered onto a web-enabled case report form using the REDCap platform. All patient data are "de-identified" such that each subject record will be labeled with only a study ID (no MRN, names, account numbers will be recorded). All clinical data will subsequently be entered into a REDCap clinical database.

All study participants will be enrolled on the Waytohealth platform where the e-triage instrument will be executed. All data at-rest is stored on encrypted disks using encryption keys managed by WaytoHealth®. Encrypted disks use AES encryption with a minimum of 256-bit keys, or keys and ciphers of equivalent or higher cryptographic strength. User passwords are never stored in clear text; they are "salted" and "hashed" to eliminate data leakage (See appendix C and section 8.1 for more on the data protections).

Patients will be tracked using blue-tooth technology while in the cancer clinic. The real-time tracking system will be executed using Link Lab's Air finder system. Only the patients deidentified research study ID will be used to link the patient and their tracked health-care time. Access to this information is visible only by the research team and will be stored on encrypted disk.

8.3 Records Retention

Records and documents pertaining to the conduct of this study, including signed consent forms, must be retained by the Investigator for the maximum period required by applicable regulations of relevant national or local health authorities.

9 Study Monitoring, Auditing, and Inspecting

9.1 Study Monitoring Plan

Overall data and safety will be monitored on an ongoing basis by the PIs and the study team. As needed, the investigators may decide to appoint an independent medical monitor to evaluate adverse events and make recommendations for continuing or stopping a trial. No interim analysis will be conducted.

9.2 Auditing and Inspecting

Participation as an investigator in this study implies acceptance of potential inspection by government regulatory authorities and applicable University compliance and quality assurance offices.

The investigator will permit study-related monitoring, audits, and inspections by the EC/IRB, the sponsor, government regulatory bodies, and University compliance and quality assurance groups of all study related documents (e.g. source documents, regulatory documents, data collection instruments, study data etc.). The investigator will ensure the capability for inspections of applicable study-related facilities (e.g. pharmacy, diagnostic laboratory, etc.).

CONFIDENTIAL

Participation as an investigator in this study implies acceptance of potential inspection by government regulatory authorities and applicable University compliance and quality assurance offices.

10 Ethical Considerations

10.1 Risks

AIM 1 Pilot study: Potential study risks are expected to be minimal. There is a minor risk of loss of confidentiality and privacy. The research team will take the necessary precautions to ensure that confidentiality and privacy are maintained. We will use commercial-grade encryption to protect participating information similar to that which is used to protect electronic medical records. Personal information will be used only by study team members who have been trained to use secure protocols to maintain the privacy of your data. Whenever possible, data will be de-identified to protect privacy. We will link individual identifying information with participant ID numbers in one secure file that will only be accessed by the study team in the case of an adverse medical event, participant dropout, or if otherwise deemed necessary by the Principal Investigator. All other identifying information will be discarded after initial contact with the research coordinator. Due to the fact, all patients will be seeing their provider with standard laboratory testing within 4 days of the questionnaire we feel that there is minimal physical risk to patients.

AIM 2 Randomized control trial: As above, there is a minimal risk of loss of confidentiality and privacy. The second potential risk is that participants misinterpret the e-triage as a means of quick communication with their care team. We will take great care to emphasize that the e-triage system is investigational, and not a replacement for usual means of communication with one's care team. Participants will be reminded repeatedly both verbally and via text after each questionnaire that they should contact their care team directly if they are having any symptoms for which they think urgent medical attention is warranted. There is also a risk of participants inappropriately, or incompletely, filing out the e-triage questionnaire. We hope to minimize this risk via the execution of the pilot study. Patients who do not fill out the questionnaire completely will therefore not be eligible to be fast-tracked to avoid an incomplete symptom assessment. Patients will be screened, per routine standard of care, by laboratory tests and vital sign assessments. Research staff will see patients at each infusion as well for toxicity assessments. Finally, patients or providers will be offered the opportunity to override the system and request in-person assessment.

